7.2 General Methodology

This is a single-center, prospective, non-randomized clinical trial designed to evaluate the technical feasibility (descriptive) of mucosal staining during CCE procedure, using MB-MMX, in CRC high risk population. As a result, the methods for analysis will be descriptive in nature (frequency and percent as well as distribution measures such as: mean, standard deviation, median and range). 95% confidence intervals (95%CI) will be presented as well.

In any case of post hoc analysis which will include statistical testing, P-value<0.05 will be considered significant.

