#### Secondary endpoint:

All AEs will be reported by number, type, relatedness (device/procedure) seriousness, severity and duration. All AEs will be captured, regardless of severity.

This section presents statistical considerations for the study design and provides a high-level description of planned analysis and reporting. More details will be given in a separate Statistical Analysis Plan (SAP) that will be approved before data freeze or lock. Any deviation to the pre-specified statistical analyses will be noted in the study report.

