#### 13.3. Primary Objective(s)

Primary Objective - to demonstrate effective polyp enhancement during a Colon Capsule Endoscopy procedure when using MB-MMX as a contrast- enhancement technique.

As this is a descriptive pilot study, no formal hypothesis was formulated. In any case of post hoc analysis which will include statistical testing, P-value<0.05 will be considered significant.

The primary objective will be measured via a subjective questionnaire, at the polyp level and at the case level:

Primary endpoint at the polyp level – the reader will answer for each polyp the following question: " was there a contrast between the polyp and the healthy mucosa? Yes/No". The endpoint refers to the percent of colonic polyps which have a visible contrast to the healthy colonic mucosa during CCE, as indicated by the reader (i.e. the reader marked "Yes"), out of the examined polyps. the percent of polyps with visible contrast will be presented with 95% confidence level (95%CI)

Primary endpoint at the case level – for each case the reader will be asked to mark the level of interference form a 5-point scale (1 =no interference to 5= high interference). The level of interference refers to the detrimental effects on the visualization of the colonic mucosa during CCE, due to use of

Version 4.0 Version Date: 16Jun2022 Page 51 of 75

MB-MMX per colonic segment (detrimental effect will be considered as any observation, such as an excessive blue dye deposit, dark and dim appearance of the tissue, interfering with tissue visualization). Analysis of this endpoint will include summary statistics (arithmetic mean, standard deviation, median and range) as well as frequency and percent of each scale level.

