7.1.3 Analysis Sets

Full Analysis Set (FAS) - includes all enrolled subjects who:

- Signed the informed consent and
- Satisfied the eligibility criteria and
- Ingested the PillCam™ COLON2 capsule

Full analysis set (FAS) will include all of the subjects the ingested the capsule and will be used for subject disposition, population and procedures description, for performance and for Safety analyses.

Per Protocol Analysis Set (PPAS) will include a subset of the FAS, which includes only subject who have demonstrated all of the following:

- Subjects' compliance to the bowel prep regimen/MB-MMX administration is ≥75% according to each of the following criteria:
 - Total volume of bowel prep material (PEG) consumed is ≥3L (out of 4L in total)
 - Intake of ≥6 MB-MMX tablets (out of total of 8 tablets)
- No major deviations related to Eligibility Criteria and/or Informed Consent.
- The capsule reached the colon during the procedure.
- Raw data has been generated for the CE procedure.

Any deviation from specified statistical plan will be in addition to "per protocol" analysis and will be reported as such. Post-hoc analysis will be conducted according to the existing data gathered, if necessary.

In addition, as there was an amendment to the CIP, and as a result, the 5 first subjects received a split dose PEG regimen and the rest received a single dose of PEG regimen, a sub-group analysis will be performed as well according to the prep regimen.

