7.5 Adjustments for Multiple Comparisons

Not applicable.

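### The plan calls any post hoc test with P<0.05 significant, in a study with no hypothesis, no stated limit on such tests and no multiplicity control (minor; a wording change)

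*SAP*

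**What the plan says.** The study is set up as descriptive. Protocol 13.3 states: "As this is a descriptive pilot study, no formal hypothesis was formulated". SAP 7.9 repeats this, and SAP 7.2 says: "As a result, the methods for analysis will be descriptive in nature". The planned outputs are percentages, summary statistics and 95% confidence intervals. No test is planned for any primary or secondary endpoint.

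Three places (Protocol 13.3, SAP 7.2 and SAP 7.9) nevertheless give a rule for unplanned tests: "In any case of post hoc analysis which will include statistical testing, P-value<0.05 will be considered significant".

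Four other provisions bear on it:

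- SAP 7.5, headed "Adjustments for Multiple Comparisons", says only that this is not applicable.
- SAP 7.1.3 (and Protocol 13.1) allows unplanned work: "Post-hoc analysis will be conducted according to the existing data gathered, if necessary". It gives no number, list of comparisons, test method or sidedness.
- Disclosure is required. SAP 7.1.3 and Protocol 13.1 say: "Any deviation from specified statistical plan will be in addition to 'per protocol' analysis and will be reported as such". Protocol section 13 adds: "Any deviation to the pre-specified statistical analyses will be noted in the study report".
- One subgroup analysis is planned in SAP 7.1.3. It sets the first 5 subjects (split-dose PEG) against the rest (single dose): "a sub-group analysis will be performed as well according to the prep regimen". No method is given.

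**The concern.** A 5% threshold limits false positives to 5% only for a test chosen before the data are seen, and only for that one test. Here the tests are by definition chosen afterwards, their number is open, and nothing adjusts for it. The plan still tells the report's author to call each result below 0.05 significant.

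Material for such tests will be on file. The reader questionnaire (Protocol Appendix D) records location, size and flat or not flat for each polyp, plus five segment scores per subject. Adverse events are collected as well. No comparison within these data is planned, so any test on them would fall under the rule.

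What is at stake is how a chance difference is described. The results may be published (Protocol 15.9), and a larger study may be considered if they are favourable (Protocol 6.2).

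**Working it through.** The documents contain no sample-size, power or family-wise error calculation, so there is no figure of the plan's own to reproduce.

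**Inputs**

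- Per-test threshold: 0.05 (Protocol 13.3, SAP 7.2, SAP 7.9).
- Adjustment: none (SAP 7.5).
- Number of post hoc tests, k: not stated. Assumed range 2 to 20.
- Subjects: up to 15, so 5 and up to 10 by regimen. Segments: 15 × 5 = 75 (SAP 7.9).

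**Step 1. Independent tests, each with a true level of 5%, all nulls true**

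Chance of at least one false significant result = 1 − 0.95^k.

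| k | Chance | Expected false positives, 0.05 × k |
|---|---|---|
| 2 | 9.8% | 0.10 |
| 5 | 22.6% | 0.25 |
| 10 | 40.1% | 0.50 |
| 20 | 64.2% | 1.00 |

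Positive correlation between tests lowers these figures. Choosing which tests to run after looking at the data raises them.

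**Step 2. Where the figures are too high: exact tests on subjects**

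Take a two-sided Fisher test of 5 against 10 subjects. Searching over the common event probability, its true level is largest at 0.5. There, the outcomes with P<0.05 carry 902 of the 2^15 = 32,768 equally likely arrangements, and 902/32,768 = 2.75%. Putting 0.0275 in place of 0.05:

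- k = 10: 1 − 0.9725^10 = about 24%, against 40.1%.
- k = 20: 1 − 0.9725^20 = about 43%, against 64.2%.

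**Step 3. Where the figures are too low: pooled segments compared between groups of subjects**

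With five segments per subject and intraclass correlation ICC, the design effect is 1 + 4 × ICC. A test that treats segments as independent, on a factor that differs between subjects, has true level 2 × [1 − Φ(1.96/√design effect)]. ICC is an assumption, since the documents give none.

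| ICC | Design effect | True level of a nominal 5% test |
|---|---|---|
| 0.1 | 1.4 | 9.8% |
| 0.3 | 2.2 | 18.6% |
| 0.5 | 3.0 | 25.8% |

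This does not carry over to comparisons between segments within the same subject.

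**Step 4. Do the disclosure clauses close the gap?**

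The clauses require the report to say that an analysis was outside the plan. They do not require it to say how many were run, they do not call the p-value nominal, and they leave the significance rule standing. A report could satisfy both sets of sentences by describing one unplanned result as post hoc and significant.

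**The case against.** The strongest reply is that the rule does little harm here. No planned analysis contains a test, so SAP 7.5 has nothing to adjust and is correct for what it covers. The post hoc sentence is conditional: it sets a threshold if a test is run and plans none. Unplanned work must be identified as such. All of this stands, and it keeps the point minor. It does not rescue the sentence, because the condition, once met, leads straight to a claim of significance.

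A reader might infer more than the documents support:

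- *That SAP 7.5 licenses unlimited testing.* The SAP does not connect the two sections. No limit is stated, which is different from permission, and post hoc work is allowed only if necessary.
- *That the regimen comparison falls under the rule.* It is pre-specified in SAP 7.1.3, so the post hoc sentence does not by its terms cover it. What is missing there is a statement that it is descriptive.
- *That chance findings could be published without any flag.* The disclosure clauses require one.
- *That post hoc p-values would decide on the larger study.* Protocol 6.2 speaks only of favourable results and does not link them to any test.

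It is also fair to object that the percentages depend on an assumed number of tests and on each test having a true 5% level. Step 2 shows that subject-level exact tests fall well short of that level.

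**Conclusion.** The point holds as an inconsistency in the written rule. A plan with no hypothesis and no multiplicity control should not declare unplanned tests significant at 0.05, and the disclosure clauses do not undo that. Severity is minor: no planned estimate, confidence interval, analysis set or safety output changes, and the pilot makes no confirmatory claim.

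The size is illustrative: 9.8% to 64.2% for 2 to 20 tests, assuming independence, a true 5% level for each test and no real effects. About 24% at ten tests is the upper figure if all were independent subject-level Fisher tests of 5 against 10. A single pooled segment test between groups of subjects that ignores clustering could already have a true level of 9.8% to 25.8% at an assumed ICC of 0.1 to 0.5.

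**What to change.** 1. In Protocol 13.3, SAP 7.2 and SAP 7.9, replace the significance sentence with: *Post hoc analyses are exploratory and are shown as estimates with 95% CIs; any p-value is nominal, labelled post hoc and reported with the number of tests run, and is not taken as evidence of statistical significance.*
2. In SAP 7.5, write: *Not applicable to the planned descriptive analyses; post hoc p-values are unadjusted and nominal.*
3. In SAP 7.1.3, state that the regimen subgroup analysis is descriptive only.

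A Bonferroni rule is no practical substitute. It needs the number of tests fixed in advance (0.05/10 = 0.005 per test for ten), and the tests here are unplanned.

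The cost is SAP wording and one protocol sentence. No data, subject or planned analysis is touched. The sponsor gives up the word significant for unplanned tests.

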7.3 Center Pooling

Not applicable, single center study

7.4 Handling of Missing, Unused, and Spurious Data and Dropouts

All available data will be included in the data listings and tabulations.

Revision 1.0

Page 6 of 7

7.5 Adjustments for Multiple Comparisons

Not applicable.

7.6 Demographic and Other Baseline Characteristics

Demographic and other characteristics will be provided. Summary statistics (arithmetic mean, standard deviation, and range for quantitative variables) will be presented for the total study population. Frequency tables for qualitative data will be provided.

7.7 Treatment Characteristics

The procedure stages will be presented as well. For example, the compliance rate for the preparation and the MB-MMX tablets intake will be reported as frequency and rate. Concomitant medications will be listed and summarized by indication.

7.8 Interim Analyses

No interim analyses are planned.

7.9 Evaluation of Objectives

Primary objectives/endpoints analysis

Polyp enhancement

For each subject, the images with polyps that were detected from the COLON2 Capsule Endoscopy procedure will be considered, i.e. the final sample size for this analysis is the number of images with polyps (one image per polyp) - the analyzed unit is the polyp image. For each polyp the reader will indicate if there was a contrast between the polyp and the healthy mucosa (yes/no). Out of the entire polyp images (from all of the subjects together), the percent of colonic polyps which have a visible contrast to the healthy colonic mucosa will be presented along 95%CI.

As this is a descriptive pilot study, no formal hypothesis was formulated. In any case of post hoc analysis which will include statistical testing, P-value<0.05 will be considered significant.

Detrimental effect

For each subject, each of the colonic segments (5 segments per subject) will be evaluated for the interference level of detrimental effects, i.e. the final sample size for this analysis will be up to 75 colonic segments - the analyzed unit is the colonic segment. For each segment the reader will indicate the level of interference according to a 5-point scale (1 =no interference to 5= high interference).

The level of interference refers to the detrimental effects on the visualization of the colonic mucosa during CCE, due to use of MB-MMX (detrimental effect will be considered as any observation, such as an excessive blue dye deposit, dark and dim appearance of the tissue, interfering with tissue visualization). Analysis of this endpoint will include summary statistics (arithmetic mean, standard deviation, median and range) as well as frequency and percent of each scale level.

The rate of colonic segments with high level of interference (i.e. 4-5 levels) out of the entire sample of segments will be presented along 95%CI.

MDT20062 SPICE Statistical Analysis Plan Revision 1.0 Page 7 of 7 Medtronic

Secondary objectives/endpoints analysis

All AEs will be reported by number, type, relatedness (device/procedure), seriousness, severity and duration. All AEs will be captured, regardless of severity. The percent of cases with at least one AE out of the total cases, will be presented with 95%CI. All of the available information will be analyzed according to the CIP criteria (inclusion, exclusion, deviations etc.).

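### SAP 7.9 puts pooled 95% CIs on polyp and segment counts with no allowance for correlation within a subject, so an ordinary binomial interval can overstate precision, most clearly for the level 4-5 segment rate

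*SAP*

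**What the plan says.** **Polyps.** SAP 7.9 makes the polyp image the analysed unit: "the final sample size for this analysis is the number of images with polyps (one image per polyp"). It then pools across subjects and gives a 95% CI: "Out of the entire polyp images (from all of the subjects together), the percent of colonic polyps which have a visible contrast". Protocol 13.3 asks for the same interval: "the percent of polyps with visible contrast will be presented with 95% confidence level (95%CI").

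**Segments.** For detrimental effects, SAP 7.9 says "the final sample size for this analysis will be up to 75 colonic segments - the analyzed unit is the colonic segment". It adds a summary with a 95% CI: "The rate of colonic segments with high level of interference (i.e. 4-5 levels) out of the entire sample of segments". The protocol does not require that interval. Section 13.3 asks only for summary statistics "as well as frequency and percent of each scale level". It introduces the endpoint as one at the case level, "for each case the reader will be asked to mark the level of interference", although the rating is made per colonic segment.

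**Interval method.** SAP 7.2 says only "95% confidence intervals (95%CI) will be presented as well". Protocol 13, 13.1 and 13.3 add nothing on how the intervals are computed. Neither document mentions a cluster, a subject-level summary, a robust or bootstrap variance, or a mixed model.

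**The concern.** An ordinary binomial interval treats every unit as an independent observation. Here the units come from at most 15 people. All polyps and segments of one subject share one bowel preparation, one tablet intake and one video, and the Appendix D questionnaire has the five segments rated on a single form. SAP 7.1.3 adds that the first five subjects had a split PEG regimen and the rest a single dose, which is another possible difference between subjects. Positive correlation within a subject is therefore plausible.

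For segments, having several units per subject is fixed by design. For polyps it depends on the data, and protocol 13.5 expects some subjects to have none.

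What is at stake is how firmly the pilot is read. Protocol 6.2 says favourable results may lead to a larger study, and an interval that is too narrow would make 15 subjects look more informative than they are.

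**Working it through.** **The plan's own figure.** 15 subjects x 5 segments = 75, which matches SAP 7.9. There is no power or sample size calculation to reproduce.

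**Inputs.** From the documents: up to 15 subjects (SAP 6), 5 segments per subject (SAP 7.9), 95% level (protocol 13.1; two-sided is assumed). Assumed, because the documents give nothing: ICC 0 to 0.5, the true rates, and the polyp layouts (a) 10 subjects x 3 polyps and (b) uneven counts 8, 6, 4, 3, 2, 2, 2, 1, 1, 1. Both layouts total 30 polyps.

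**Effective sample size.** Design effect DE = 1 + ICC x (sum m^2 / sum m - 1), where m is the number of units per subject; effective n = n / DE.
- Segments: DE = 1 + 4 x ICC = 1.4, 2.2, 3.0 at ICC 0.1, 0.3, 0.5. Effective n = 75/DE = 53.6, 34.1, 25.
- Polyps (a): DE = 1 + 2 x ICC = 1.2, 1.6, 2.0. Effective n = 25, 18.8, 15.
- Polyps (b): sum m^2 = 140 and 140/30 = 4.67, so DE = 1 + 3.67 x ICC = 1.37, 2.10, 2.83. Effective n = 21.9, 14.3, 10.6.

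**Coverage of the ordinary exact (Clopper-Pearson) 95% interval.** Beta-binomial simulation, 20,000 runs per cell, so the standard error is at most sqrt(0.25/20000) = 0.35 points.

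| Layout, true rate | ICC 0 | 0.1 | 0.3 | 0.5 |
|---|---|---|---|---|
| Segments 15 x 5, 20% | 95.6% | 91.2% | 82.3% | 74.5% |
| Polyps (a), 70% | 97.4% | 95.7% | 91.9% | 88.2% |
| Polyps (a), 90% | 99.2% | 98.5% | 96.9% | 95.6% |
| Polyps (b), 70% | 97.4% | 94.3% | 87.5% | 80.6% |

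Over true segment rates of 10% to 30%, coverage runs from about 93% (ICC 0.1) to 75% (ICC 0.5). Polyps (b) at 90% contrast run from 98% to 92%. Where polyps are few and even and contrast is high, the exact interval is conservative enough to absorb the correlation.

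The simulation gives all five segments the same true rate. With strong systematic differences between segments, coverage in one run rose from 82% to 86%, so this offsets only part of the loss.

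**A clustered interval, worked through.** With J contributing subjects, y_j positive out of m_j, n = sum m_j and pooled percent p:

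V = J/(J-1) x sum(y_j - p m_j)^2 / n^2

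effective n = p(1-p)/V x (t[n-1]/t[J-1])^2, with 97.5% t quantiles, capped at n.

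An exact interval is then computed on the effective n.

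- *Segments:* 15 of 75 at level 4-5, spread 4, 3, 3, 2, 1, 1, 1 over seven of 15 subjects. p = 0.20 and p m_j = 1. The sum of squares is 9+4+4+1+0+0+0+8x1 = 26. V = (15/14) x 26/5625 = 0.00495. 0.16/V = 32.3; x 0.863 = 27.9. Ordinary interval 11.6% to 30.8%; clustered 7.4% to 39.4%.
- *Polyps:* 24 of 30 with contrast; 1, 1, 2, 2 in four subjects and 3 in each of six. p = 0.80 and p m_j = 2.4. The sum of squares is 2x1.96 + 2x0.16 + 6x0.36 = 6.40. V = (10/9) x 6.40/900 = 0.0079. 0.16/V = 20.2; x 0.817 = 16.6. Ordinary interval 61.4% to 92.3%; clustered 53.5% to 95.2%.

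In simulated samples whose units are not all the same, at ICC 0.1 to 0.5, this interval covers 91% to 97% for segments. For polyps (a) it covers 98% to 97% at 70% contrast, and for (b) 97% to 94%. At 90% contrast it covers about 99% in both.

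**The case against.** **The SAP prescribes no formula.** A reader might infer that the SAP lays down a binomial interval. It does not: no method is named, and the choice of analysed unit fixes the denominator, not the variance. This stands. The defect is an omission. But the text calls the unit counts the final sample size and nothing points a programmer elsewhere, so the binomial interval is what the plan would naturally yield.

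**The study is descriptive.** There is no hypothesis, margin or success rule, and the level 4-5 interval is an SAP addition. This stands too and limits the consequence. Still, the sponsor chose to report intervals, conveying precision is their only job, and one belongs to a primary endpoint. Any post hoc test at P<0.05 on the same units would share the problem.

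**The size rests on assumptions.** True. A reader might infer that both intervals are bound to be too narrow. The results do not support that: with 10 x 3 polyps at 90% contrast, coverage stays at 96% or more. Nor should a case of one subject with 25 polyps lead the argument. FAP eligibility and the 25-row form allow it, but nothing shows it is likely.

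**A clustered interval has its own costs.** Also true; they are listed with the change below.

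**Conclusion.** The gap is real and worth closing before the SAP is applied. It is clearest for the level 4-5 segment rate, where five units per subject are built in: about 93% to 75% coverage at assumed ICC 0.1 to 0.5, somewhat better if segments differ systematically. For polyps the loss runs from none or slight (few, evenly spread, high contrast) to about 80% coverage in the uneven layout at 70% contrast and ICC 0.5. At ICC 0 there is no loss. A positive ICC is plausible but not documented, and every ICC, rate and layout used here is an assumption.

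A reader might take this to mean that the pooled percents are wrong or the pilot invalid. Neither follows. The percents and their weighting by unit count stand; only the stated precision is in question, and no decision rule depends on it.

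**What to change.** Change SAP 7.9 only:

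- Keep both pooled percents and state that both 95% CIs treat the subject as the cluster. One workable choice is the exact interval on an effective sample size shown above, with the t correction and the cap at n, labelled approximate.
- When all units score the same, the correlation cannot be estimated. Show the exact limits on n and on the number of contributing subjects J, as the bounds for independence and for complete agreement within subjects. For 30/30 polyps in 10 subjects the lower limits are 88.4% and 69.2%; for 0/75 segments in 15 subjects the upper limits are 4.8% and 21.8%.
- Always report the number of contributing subjects and the units per subject.

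No protocol amendment is needed. Protocol 13 leaves analysis detail to the SAP, and the interval requested in 13.3 can be a clustered one. Editing 13.3 would bring in the submission and approval steps of 15.6 for no gain.

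The cost is SAP wording and a few lines of code, with no new data. The SAP should also state the downsides:

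- Intervals widen even at ICC 0: mean width about 19 to 21 points for segments at 20%, and 34 to 39 for 10 x 3 polyps at 70%. At ICC 0.3 the figures are 19 to 30 and 34 to 47.
- The interval is conservative at high contrast (about 99% coverage at 90%).
- It still under-covers if one subject dominates: 83% to 94% when one subject holds 25 of 40 polyps.

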#### **Procedure related risks:**

#### **Bowel preparation risks:**

As the study procedure involves bowel preparation, additional risks are anticipated.

Some bowel-cleansing preparation agents may involve risks of dehydration (loss of body water) and/or imbalance in the levels of salts in the bloodstream. These risks may be further avoided by strictly following the instructions, such as carefully drinking the amounts of fluids required before and during the capsule preparation procedure.

Due to bowel preparation the subject might experience abdominal pain, headache, vomiting, nausea, gagging, bloating, significant anal burning/irritation, hemorrhoids bleeding, dizziness, fatigue, which are anticipated symptoms, mostly mild, that could be related to the bowel preparation procedure. Another risk is possible allergic reaction to bowel preparation agents.

MDT20062 SPICE Clinical Investigation Plan			
Version 4.0	Version Date: 16Jun2022	Page 36 of 75	Medtronic

For further information and complete list of adverse events, please refer to the bowel preparation agents' leaflets/manuals for use.

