#### 12. Adverse Events and Device Deficiencies

#### 12.1. Adverse Events

AEs definitions are provided in Table 3- Adverse Event and Device Deficiency Definitions.

Adverse Events will be collected for all enrolled subjects at the start of the bowel preparation, at day (-1), until the follow-up phone call (visit 3). Medical care will be provided, as defined in the informed consent, for any AE related to study participation, if needed.

Reporting of these events to the Sponsor will occur on an AE Form. Each event must be reported separately. Documented pre-existing conditions are not considered AEs unless the nature or severity of the condition has worsened. Also, Diarrhea<24h after the CCE and mild anal burning/irritation are considered as the expected outcome of the bowel preparation process and shall not be recorded as Adverse Events, as long as the event does not require any medical intervention. Incidental findings observed during CCE video analysis will not be considered as AEs and will not be reported as such. In addition, in case of discovering a pregnancy during the course of the study, it will not be considered as an AE and will not be reported as such.

Per ISO14155:2020, it is required to collect all AEs and DDs. Non-subject AEs are not expected in this study, thus are not collected.

For AEs that require immediate reporting, initial reporting may be done by phone, fax, or on the eCRF completing as much information as possible. The completed AE eCRF must be submitted to the Sponsor as soon as possible.

Any medication/treatment associated with the treatment of an AE must be reported.

Subject deaths are also required to be reported. Refer to Section 12.6 for Subject Death collection and reporting requirements.

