**Table 3- Adverse Event and Device Deficiency Definitions** 

	General
Adverse Event (AE)	Untoward medical occurrence, unintended disease or injury, or untoward clinical signs (including abnormal laboratory findings) in subjects, users or other persons, whether or not related to the investigational medical device and whether anticipated or unanticipated  NOTE 1: This definition includes events related to the investigational medical device or the comparator.  NOTE 2: This definition includes events related to the procedures involved.  NOTE 3: For users or other persons, this definition is restricted to events related to the use of investigational medical devices or comparators.  (ISO 14155:2020, 3.2)
Adverse Device Effect (ADE)	AE related to the use of an investigational medical device  NOTE 1: This definition includes AEs resulting from insufficient or inadequate instructions for use, deployment, implantation, installation, or operation, or any malfunction of the investigational medical device.  NOTE 2: This definition includes any event resulting from use error or from intentional misuse of the investigational medical device.  NOTE 3: this includes 'comparator' if the comparator is a medical device.  (ISO 14155:2020, 3.1)

MDT20062 SPICE Clinical Investigation Plan			
Version 4.0	Version Date: 16Jun2022	Page 40 of 75	Medtronic

Inadequacy of a medical device with respect to its identity, quality, durability, reliability, usability, safety or performance.  NOTE 1: DD include malfunctions, use errors and inadequacy in the information supplied by the manufacturer including labeling.  NOTE2: This definition includes device deficiencies related to the investigational medical device or the comparator. (ISO 14155:2020, 3.19)
Relatedness
An AE that results from the presence or performance of any component of the device.  Device-related: An AE that results from the presence or performance (intended or otherwise) of the device.
An AE that occurs due to any procedure related to the CCE procedure (other than device). The preparation procedure for the CCE procedure in the study includes consumption of bowel preparation materials and MB-MMX tablets (non-MDT products).
Seriousness

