SOVERE	Event results in significant symptoms that prevents normal daily activities may require hospitalization or invasive intervention (e.g., anemia resulting in blood transfusion).

An AE can be classified as severe and not deemed an SAE. Similarly, an SAE is not automatically severe in nature. Severity will be assessed by the Investigator.

Regardless of severity, all AEs occurring during the study must be recorded in the subject's eCRF. The following information and assessments should be documented:

- Type of event (AE term)
- Subject number
- Date of AE onset

 Version 4.0
 Version Date: 16Jun2022
 Page 43 of 75
 Medtronic

- Date of resolution
- Seriousness
- Severity degree: mild / moderate / severe
- Relationship to study device and procedure: causal relationship/ probable/ possible/ not related
- Measures taken
- Outcome of event:
  - not recovered/ not resolved
  - recovered/resolved
  - recovered/ resolved with sequelae
  - recovering/ resolving
  - unknown
  - fatal

The sponsor shall immediately conduct an evaluation of any unanticipated events if determined that the events presents an unreasonable risk to subjects and report the results of such evaluation per the local requirements.

In case of SAEs and SADEs, the following emergency contact may be approached:

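### Does the SAP's promise to capture all AEs leave the any-AE percentage undefined, given the protocol's exemption for mild anal burning and some diarrhea?

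*SAP*

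**What the plan says.** SAP section 7.9, on the secondary objective, reads: "All AEs will be captured, regardless of severity. The percent of cases with at least one AE out of the total cases". A 95% confidence interval accompanies the percentage. Protocol section 12.5 gives the matching instruction for the eCRF: "Regardless of severity, all AEs occurring during the study must be recorded".

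Protocol section 12.1 carves out two effects. The first is "Diarrhea<24h after the CCE". The second follows directly, with the rule for both: "mild anal burning/irritation are considered as the expected outcome of the bowel preparation process and shall not be recorded as Adverse Events". The exemption lapses if the event needs medical intervention. The same section opens AE collection at the start of bowel preparation on Day -1 and closes it at the follow-up call.

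Protocol Table 3 defines an AE as an untoward occurrence, "whether or not related to the investigational medical device and whether anticipated or unanticipated", and its second note adds: "This definition includes events related to the procedures involved". Protocol section 11.1 lists "significant anal burning/irritation" among the anticipated symptoms of bowel preparation. It names chromaturia and discolored feces as the most common events with MB-MMX, and no exemption covers those two.

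**The concern.** SAP 7.9 and protocol 12.5 say severity does not decide what is recorded. For anal burning, protocol 12.1 makes severity decide. Table 3 seems to close off the defence that an expected effect is no AE. Protocol section 14.1, which lists departures from ISO 14155 AE handling, names only non-subject AEs and USADEs. The SAP mentions neither exemption.

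This is the one safety percentage for which SAP 7.9 names an interval. If the site and the analyst followed different passages, its numerator would be ambiguous. Events never recorded cannot be found later in listings or severity tables. A report that repeated the SAP sentence would claim complete capture when the site had been told to leave out two kinds of event.

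**Working it through.** The documents state no expected AE rate or interval width, so there is no figure to reproduce. The check is mainly a comparison of texts, followed by a sense of scale.

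**1. Which text governs the two named effects?** Protocol 12.1 is a specific instruction about named events. The phrases about all AEs in SAP 7.9 and protocol 12.5 are general. The SAP says it was formulated from CIP version 4.0, and its sentence repeats the endpoint wording in protocol sections 5.1.2, 13 and 13.4. An AE in the SAP is therefore an event that the protocol treats as an AE. Mild anal burning, and diarrhea less than 24 hours after the procedure, are outside the numerator unless intervention was needed.

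**2. Do the supporting passages contradict that?**
- Section 11.1 lists only the significant form of anal burning, which agrees with exempting only the mild form.
- Table 3 first requires an untoward occurrence. Whether the event was anticipated comes second. Section 12.1 classes the two effects as the expected result of a purgative, so treating them as not untoward is a tenable reading.
- Section 14.1 is not an index of what 12.1 leaves out. Section 12.1 also removes unchanged pre-existing conditions, incidental video findings and pregnancy, and 14.1 lists none of these.

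**3. What stays open?** Diarrhea before the period that the exemption describes. From protocol Appendix A, PEG starts at 18:00 on Day -1 and the capsule is taken at about 08:00 on Day 0, which is 14 h. From section 10.4, the recorder may stay on for up to 12 h after ingestion in subjects sent home. If the procedure is taken to end at recorder removal (an assumption, since the protocol does not say), the stretch is 14 + 12 = 26 h at most. The wording also does not say whether the 24 hours refer to onset or duration.

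**4. Scale.** Take n = 15, the maximum enrolment. One subject is 1/15 = 6.7 percentage points. The documents name no interval method. Assuming Clopper-Pearson, the lower limit is the 0.025 quantile of Beta(k, n − k + 1) and the upper limit is the 0.975 quantile of Beta(k + 1, n − k), with an upper limit of 100% when k = n.

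| Subjects with a recorded AE | Percent | Exact 95% CI |
|---|---|---|
| 3/15 | 20.0 | 4.3 to 48.1 |
| 6/15 | 40.0 | 16.3 to 67.7 |
| 9/15 | 60.0 | 32.3 to 83.7 |
| 12/15 | 80.0 | 51.9 to 95.7 |
| 15/15 | 100 | 78.2 to 100 |

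All counts are assumptions. If 3 subjects had other AEs and 3 more had only preparation-period diarrhea, the choice of reading moves the result from 20.0% to 40.0%. If 12 subjects already had another recorded AE, at most 15 − 12 = 3 could be added, moving it from 80.0% to 100%. A subject with chromaturia or discolored feces is already in the numerator, so the more common those are, the less room is left for the open events to matter.

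**The case for a change.** The best case for a change rests on preparation-period diarrhea. Collection is open from Day -1. Read literally, the exemption does not reach back that far; read by its stated reason, it does. SAP 7.9 refers to analysis by CIP criteria, but its examples are eligibility and deviations, and in any case it cannot resolve an ambiguity inside the protocol. Section 12.1 itself also says that ISO 14155 requires all AEs to be collected. The SAP plans a subgroup analysis of the first 5 subjects, on split-dose PEG, against the rest; if that covers safety, preparation timing enters the comparison. The remedy would be cheap: one sentence, one footnote and one query to a single site.

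Much of this stands as description. SAP 7.9 does not cite the exemption, its wording sits badly beside an exemption for mild events, and preparation-period diarrhea is not clearly addressed. It does not follow that the SAP should change. The SAP analyzes what the site recorded. It cannot set a start and end for the exemption that the protocol does not give, least of all when it already describes the first 5 subjects as having received their regimen. Events left unrecorded would stay unrecorded. A sentence that chromaturia counts would add nothing, because nothing excludes it.

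**Conclusion.** No change is needed. For the two effects named in protocol 12.1 the numerator is settled: they are not counted unless they needed medical intervention. The friction in wording lies within the protocol, and the SAP inherits it.

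The remaining gap is missing detail about diarrhea during preparation and the procedure. Each subject whose only event falls there is worth 6.7 points at n = 15. How many there would be is unknown, because the documents give no rate. The result is a descriptive percentage in a pilot of up to 15 subjects, with no hypothesis and no decision threshold, and the interval is wide on either reading. An analyst would ordinarily footnote the AE tables with the protocol's recording rule and say how the site handled preparation-period diarrhea. That labels the percentage correctly without a plan revision.

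This conclusion assumes that a specific recording rule prevails over a general statement, and that the any-AE percentage is used only descriptively, as both documents state.
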